10.6.2 Prevention and Toxicity Management of Risks for AZD4573 Monotherapy

This section provides recommendations for treatment of potential toxicities associated with AZD4573, and guidance about modifying the dose of AZD4573 due to those toxicities. For complete safety information refer to the IB for AZD4573.

Generally, Grade 1 or 2 non-haematological and/or haematological toxicities do not require AZD4573 dose reductions and should be managed as medically indicated (with or without short dose interruptions) by the treating physician. Grade 3 and 4 toxicities require dose modifications, temporary treatment interruptions, or discontinuation of AZD4573. These are described in [Table 11](#) and [Table 12](#) in the Section [10.6.1](#) (Dose Modification – Module 1).

10.6.2.1 Tumour Lysis Syndrome (TLS)

Tumour lysis syndrome is an important identified risk for AZD4573. **TLS prophylaxis is mandatory for all participants** starting 3 days before the first dose of AZD4573, which should be followed in addition to institutional guidelines.

Tumour lysis syndrome is characterised by the rapid and/or massive release of intracellular constituents (potassium, phosphorus and nucleic acids that can be metabolised to uric acid) following tumour cell lysis, resulting in life-threatening complications including acute kidney injury, arrhythmias, and neurological complications. While TLS can be seen in solid tumours, it is most prevalent in haematological malignancies. Prevention and management of TLS is dependent on risk stratification, and risk-based prophylaxis and management (Howard et al 2016). Participants identified with TLS potential per published risk guidelines (Coiffier et al 2008; Table 13) should be provided with adequate hydration, pharmacological pretreatment with allopurinol or rasburicase, and be carefully monitored for development of TLS. The risk of TLS associated with AZD4573 is anticipated to be lower for participants with PTCL or cHL compared to participants with DLBCL, as TLS is less often seen in these populations (Gopal et al 2015; Chen et al 2017; Coiffier et al 2014; O'Connor et al 2015; O'Connor et al 2011) .

The Howard modification of the Cairo-Bishop definitions of clinical and laboratory TLS are included in [Appendix G](#). Laboratory or clinical TLS may trigger dose modification in accordance with guidelines provided in [Table 11](#).

10.6.2.1.1 TLS Prophylaxis

Tumour lysis syndrome (TLS) prophylaxis is mandatory for **all** participants starting 3 days before the first dose of AZD4573. TLS prophylaxis is mandatory for all infusions as outlined below in [Table 13](#) which provides TLS prophylaxis guidance, which should be followed in addition to institutional guidelines. In the event of a discrepancy between the protocol guidelines for the management of TLS and the Institutional guidelines of a given investigator/centre, the investigator should discuss with the Study Physician.

In addition to the criteria outlined in [Table 13](#) below, any participant with creatinine clearance (CrCL) < 80 mL/min must be considered at higher risk of developing TLS and managed appropriately.

TLS prophylaxis/management with rasburicase and IV fluid is permitted at any time during screening and treatment, however rasburicase and allopurinol must not be co-administered (Jones et al 2015).

It is strongly recommended that for all participants with elevated uric acid (hyperuricaemia) and intermediate/high risk of TLS, rasburicase (0.20 mg/kg/d IV over 30 minutes) should be administered as prophylaxis prior to AZD4573 and repeated as clinically indicated thereafter as per local standard.

NOTE: If hyperuricaemia is present at screening and/or during ramp-up, SoC therapy should be administered (including IV fluid and rasburicase or allopurinol) to reduce the uric acid levels to < ULN before each administration of AZD4573. Rasburicase and allopurinol must not be co-administered.

Table 13 Mandatory TLS Prophylaxis Guidance (in Addition to Institutional Guidance)

Intermediate to High Risk	
LDH > ULN OR any lymph node ≥ 5 cm	
Prophylaxis	
Hydration ^a	Oral (1.5-2 L/day) plus additional IV fluid: Normal saline 500 mL over 2 to 4 hours prior to AZD4573, then 100 to 175 mL/h as tolerated to maintain urine output.
Antihyperuricemics	Allopurinol 300 mg orally twice daily beginning 3 days prior to AZD4573 and continuing at least through the end of Week 1b. Consider prophylactic rasburicase if baseline uric acid is elevated above ULNd, LDH > 2 × ULN, or high tumour burden.

^a Administer more aggressive IV fluid hydration for any participant who cannot tolerate or maintain oral hydration.

^b After the end of Week 1, or upon discussion and agreement with the Study Physician, the dose or frequency of allopurinol may be reduced. Note: The dose of allopurinol should be reduced for renal insufficiency.

^c The recommended dose for rasburicase is 0.20 mg/kg IV over 30 minutes. Rasburicase is contraindicated in participants with G6PD deficiency, so participants at higher risk for G6PD deficiency (eg, African or Mediterranean ancestry) should be screened for this condition prior to starting rasburicase. Rasburicase and allopurinol must not be co-administered.

^d Uric acid levels should be < ULN before each dosing of AZD4573.

Adequate supportive therapy as per Institutional guidelines should be given for all toxicities.

NOTE: TLS prophylaxis/management with rasburicase and IV fluid is permitted at any time during screening and treatment. Rasburicase and allopurinol must not be co-administered.

Abbreviations: h, hour; IV, intravenous; LDH, serum lactate dehydrogenase; ULN, upper limit of normal.

Modified from [Coiffier et al 2008](#).

10.6.2.1.2 TLS Monitoring and Management

Please refer to [Appendix G](#) for the definition of TLS and the TLS grading criteria to be used in this study.

All participants will receive TLS prophylaxis during the intra-participant dose ramp-up and be monitored for TLS during the first 24 hours post start of infusion during the intra-participant dose ramp-up (see Sections [10.6.2.1.1](#) and [10.6.2.1.2](#)). If there are no signs of TLS at the 6 hour TLS monitoring assessment, the participant can be managed as an outpatient at the discretion of the investigator and return to the clinic the next day to complete the 24 hour TLS monitoring assessment. Participants showing signs of TLS at 6 hours after the start of infusion must remain admitted for inpatient TLS monitoring approximately every 6 hours (or more frequently if clinically indicated) until the 24 hour TLS monitoring assessment.

Where hospitalisation for longer than the mandated 24 hours is required it should be noted that if this is due to occurrence of an AE then the event must be reported as an SAE, per definition. However, if it is purely for the purposes of extended observation then this does not qualify as an SAE and does not need to be reported.

For all participants, results of safety laboratory testing (haematology and clinical chemistry at a minimum) must be available within 72 hours prior to dosing and must be reviewed by the investigator prior to each administration of AZD4573. For each TLS monitoring timepoint, a TLS Monitoring page in the eCRF is to be filled out.

In particular, the uric acid level must be < ULN prior to the start of each AZD4573 infusion.

It is strongly recommended that for all participants with elevated uric acid (hyperuricaemia) and intermediate/high risk of TLS, prophylaxis should be administered prior to AZD4573 per Section 10.6.2.1.1 and repeated as clinically indicated thereafter as per local standard.

Monitoring for TLS includes checking potassium, calcium, phosphate, uric acid, and creatinine. Fluid balance must be monitored according to institutional standards.

Any participant developing laboratory TLS must be treated promptly for electrolyte abnormalities (such as hyperkalaemia) to prevent arrhythmias/seizures and for elevated uric acid (hyperuricaemia) with rasburicase (0.20 mg/kg/d IV over 30 minutes for up to 5 days) to prevent acute renal failure and monitored closely for signs of progression to clinical TLS.

If these measures are inadequate, then haemodialysis represents definitive therapy and should be initiated promptly.

Any participant with hyperkalaemia should receive cardiac monitoring with continuous telemetry for ECG changes associated with potentially life-threatening arrhythmias.

Participants with TLS or suspicion of TLS will remain in hospital to undergo additional investigations until the TLS has resolved.

10.6.2.1.3 Management of Hydration

Adequate fluid intake for all participants enrolled into the study is mandatory, in particular, around the times of AZD4573 dosing.

All participants are **mandated** to receive IV fluid hydration with normal saline (NaCl 0.9%). For participants at intermediate or high risk for TLS (per Table 13), normal saline 500 mL should be administered over 2 to 4 hours prior to AZD4573 and then continued at a rate of 100 to 175 mL/hr as tolerated to maintain urine output at least until the 6 hour TLS monitoring lab assessment, and thereafter if medically indicated.

In case of diarrhoea/nausea/vomiting, more aggressive IV fluid hydration may be needed as clinically indicated. Participants are also encouraged to drink enough fluid before and after each dosing. Please use diuretics carefully; do not use them prophylactically, only if participants have signs of hyper-hydration.

10.6.2.2 Transaminases Increase With or Without Concomitant Bilirubin Increase and the Risk of Liver Injury

Transaminase elevations are an important identified risk for participants treated with AZD4573. Evidence of abnormal liver function should be monitored as per the protocol guidelines. Increased levels of AST, ALT, or serum bilirubin should trigger an investigation of the cause, which may include viral infection or disease progression with liver infiltration. The investigator should consider whether the abnormal liver chemistry test results meet the criteria for expedited reporting.

Bilirubin increase with transaminase increase (ALT or AST or both) is included as an important identified risk for AZD4573. Biochemical changes of increased transaminases with concomitant increase in bilirubin fulfilling criteria for potential Hy's law have been observed in participants treated with AZD4573. These events resolved rapidly and have to date not been associated with any adverse clinical sequelae or lasting liver damage. Upon re-challenge with AZD4573, there is no consistent pattern of recurrence, nor is there any consistent increase in severity of the events. As such, whilst the events follow the biochemical definition of Hy's law, the clinical pattern is rapidly self-limiting and does not seem to predict any lasting liver damage.

Liver injury is classified as an important potential risk for AZD4573. Participants who experience increases in transaminases or bilirubin levels after AZD4573 dosing must be monitored in line with Section 10.8.2.5. Please refer to Section 10.6.1 (dose modification and re-treatment) for additional information on how to manage a participant with increases in transaminases/bilirubin.

Additional **CCI** [REDACTED] will also be collected for central analysis (see Section 10.8.9.3).

If bilirubin fails to resolve within 96 (-2/+12) hours or transaminases fail to resolve within 7 days, or if the event is associated with significant clotting abnormality or clinical symptoms of liver disease, study treatment must be permanently discontinued (the participant remains on study for the 30-day Follow-up and LTFU visits), and the event must be immediately communicated to AstraZeneca.

For guidance on treating liver toxicity, please refer to Section 10.6.2, Table 12.

During the course of the study the investigator will remain vigilant for increases in liver

biochemistry. The investigator is responsible for determining whether a participant meets PHL criteria at any point during the study.

[Appendix E](#) describes the process to be followed to identify and appropriately report cases of PHL. It is not intended to be a comprehensive guide to the management of elevated liver biochemistries.

The investigator will participate, together with the Study Physician, in review and assessment of cases meeting PHL criteria to agree whether HL criteria are met.

The investigator is responsible for recording data pertaining to PHL/HL cases and for reporting AEs and SAEs according to the outcome of the review and assessment in line with standard safety reporting processes.

Available transcriptomic and clinical pathology data from the FIH study of AZD4573 monotherapy suggests the presence of an acute phase response in participants showing signs of liver injury. Thus, anti-inflammatory prophylaxis with steroids (eg, dexamethasone) could be expected to have a beneficial effect on the incidence and severity of adverse effects on the liver related to AZD4573. While, in the absence of a suitably-sized control group without prophylactic steroid administration, there is no confirmatory evidence for a positive effect of dexamethasone on liver safety profiled from available FIH study clinical data as yet. Assessment of ALT changes from baseline versus cumulative dexamethasone dose suggests a possible trend towards a negative correlation, ie, high dexamethasone doses being associated with smaller increases in ALT post-baseline.

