10.6.1 Dose Modification

Dose modification and discontinuation guidelines for haematological and non-haematological toxicities (excluding abnormal liver chemistry test results) are shown below in [Table 11](#). Dose modifications for AZD4573 for abnormal liver chemistry test results are described in [Table 12](#).

In general, if a participant experiences a Grade 1 or Grade 2 haematological or non-haematological toxicity, no dose modification is required. If a participant experiences a Grade 3 or Grade 4 toxicity, not attributable to the disease or disease-related processes under investigation, dosing will be interrupted and/or the dose reduced (see [Table 11](#) for recommended dose modifications for AZD4573) and supportive therapy administered as required. If the toxicity resolves or reverts in line with the dose modification guidelines below and the participant was showing clinical benefit, treatment with study treatment(s) may be restarted.

If the toxicity does not resolve in line with the dose modification guidelines below, then the participant should be discontinued from the study treatment and observed until resolution of the toxicity. Maximal drug interruption allowed for AZD4573 is 21 consecutive days; in cases where more than 21 days are needed, a decision to continue, modify, or discontinue study treatment will be made on a case-by-case basis in consultation with the principal investigator and the Study Physician.

Table 11 Recommended Dose Modifications for AZD4573

Event ^a	Occurrence	Action with AZD4573	
Tumour Lysis Syndrome (TLS)			
Changes in uric acid, potassium, phosphorus, creatinine or calcium, or symptoms suggestive of TLS	Any	For any abnormal changes present before dosing, initiate supportive therapy and hold drug for up to 7 days. If not resolved, reduce by 1 dose level.	
		For events of Howard Grade 1 or 2 TLS, resume at same dose level upon resolution.	
		For first occurrence of Howard Grade 3 TLS resume at the same dose upon resolution to Grade 1.	
		For second occurrence of Howard Grade 3 TLS, after resolution to Grade 1, reduce dose by 1 dose level when re-starting AZD4573 except events that in the opinion of the investigator, in consultation with the Study Physician, are not dose limiting.	
		For subsequent occurrences of Howard Grade 3 TLS, further re-challenge and dose level to be discussed with the Study Physician.	
For events of Howard Grade 4 TLS, discontinue AZD4573.			

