Grade 3 thrombocytopenia without bleeding	Any	Withhold AZD4573 until Grade \leq 2 or baseline level. Restart AZD4573 at the same dose level.
Grade 4 thrombocytopenia without bleeding requiring blood or platelet transfusion	First occurrence	Withhold AZD4573 until Grade \leq 2 or baseline level. Restart AZD4573 at the same dose level.
	Second occurrence	Withhold AZD4573 until Grade \leq 2 or baseline level. Restart AZD4573 with 1 level dose reduction. If not recovered to Grade \leq 2 or baseline level discontinue.
	Third occurrence	Discontinue AZD4573.
Grade 3 or 4 thrombocytopenia with bleeding requiring blood or platelet transfusion	First occurrence	Withhold AZD4573 until Grade \leq 2 or baseline level. Restart AZD4573 with 1 level dose reduction. If not recovered to Grade \leq 2 or baseline level discontinue.
	Second occurrence	Discontinue AZD4573.

^a Adverse reactions are graded using NCI CTCAE version 5.0.

^b In cases where more than 21 days are needed, a decision to continue, modify, or discontinue study treatment will be made on a case-by-case basis in consultation with the principal investigator and the Study Physician.

Abbreviations: ANC, absolute neutrophil count; ASCO, American Society of Clinical Oncology; ESMO, European Society for Medical Oncology; G-CSF, granulocyte-colony stimulating factor.

Dose modifications for AZD4573 for abnormal liver chemistry test results are described in [Table 12](#).

Table 12 Recommended Dose Modifications for AZD4573 for Abnormal Liver Chemistry Test Results

Event ^a	Action
Isolated^b elevations in ALT, AST, or bilirubin	
Grade 1 Isolated ALT/AST \leq 3 \times ULN or Isolated Bilirubin \leq 1.5 \times ULN	Maintain current dose level. Monitor ALT, AST, ALP, and bilirubin at least 1x per week.

Event ^a	Action
Grade 2 Isolated ALT/AST > 3 to $\leq 5 \times$ ULN or Isolated Bilirubin > 1.5 to $\leq 3 \times$ ULN	After 7 days if hepatic enzymes resolve to Grade ≤ 1 , re-challenge at same dose level.
Grade 3 Isolated ALT/AST > 5 to $20 \times$ ULN	If recovered to Grade ≤ 1 within 7 days, allow re-challenge at same dose level. If not recovered to baseline level within 7 days, discontinue AZD4573.
Grade 3 Isolated Bilirubin > 3 to $10 \times$ ULN	If recovered to baseline level within 96 hours (-2/+12 hours) of start of dose allow re-challenge at same dose level. If not, discontinue AZD4573.
Grade 4 Isolated ALT > $20 \times$ ULN or Isolated Bilirubin > $10 \times$ ULN	Discontinue AZD4573.

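### Section 10.6.2.2 sets a mandatory liver stopping rule with no grade threshold and no definition of *resolve*; for isolated Grade 2 bilirubin clearing after 108 hours but by day 7, it contradicts Table 12

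*Protocol*

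**What the plan says.** **Section 10.6.2.2.** "If bilirubin fails to resolve within 96 (-2/+12) hours or transaminases fail to resolve within 7 days", or if there is a significant clotting abnormality or clinical symptoms of liver disease, then "study treatment must be permanently discontinued". The sentence names no CTCAE grade and no multiple of ULN. It does not say what counts as resolved or when the clock starts. The next line adds: "For guidance on treating liver toxicity, please refer to Section 10.6.2, Table 12".

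**Section 10.6.1, Table 12, isolated elevations.**
- Grade 1: "Maintain current dose level. Monitor ALT, AST, ALP, and bilirubin at least 1x per week". No time limit.
- Grade 2 (ALT/AST >3 to 5 x ULN, or bilirubin >1.5 to 3 x ULN): the row opens "After 7 days if hepatic enzymes resolve to Grade" 1 or lower, and then permits re-challenge at the same dose. It gives no action if the rise has not resolved, and no 96-hour limit for bilirubin.
- Grade 3 ALT/AST: "If not recovered to baseline level within 7 days, discontinue AZD4573".
- Grade 3 bilirubin: "If recovered to baseline level within 96 hours (-2/+12 hours) of start of dose allow re-challenge at same dose level"; otherwise discontinue.

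**Table 12, concurrent elevations.** The 96-hour and 7-day limits apply at ALT or AST of at least 3 x ULN with total bilirubin of at least 2 x ULN. A 7-day limit also applies to Grade 3 ALT or AST with a smaller bilirubin rise.

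**Section 10.6.1, general text.** As a general rule, "if a participant experiences a Grade 1 or Grade 2 haematological or non-haematological toxicity, no dose modification is required". The same section sends liver chemistry to Table 12.

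**The concern.** Two passages govern the same event. One is mandatory and ungraded; the other is graded and, at low grades, either keeps the dose or allows it to restart. Two sites could therefore stop one participant permanently and continue another with the same laboratory course.

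The stop cannot be undone: Section 7.1 does not allow a participant taken off treatment for safety reasons to restart it. Transaminase increase, and bilirubin increase with transaminase increase, are listed in Table 2 as important identified risks, so liver findings are expected.

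The choice of passage also reaches the analysis. Under Section 8.3.5, a laboratory deterioration becomes a reportable adverse event if it is the reason for stopping treatment. A low-grade rise that would otherwise go unreported could thus enter the tables of adverse events leading to discontinuation (SAP Section 5.6.2.2) because of the passage the site followed. If judged related, it also counts toward the >25% trigger in Sections 7.1.1, 10.4.1 and 10.4.4.

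**Working it through.** The plan has no figure to reproduce here. The check sets the passages side by side.

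| Course after dosing | Section 10.6.2.2 | Table 12 | Result |
|---|---|---|---|
| Isolated Grade 1, persisting past the limit | Stop if *resolve* means baseline; no stop if it means Grade 1 or lower | Keep dose | Depends on the undefined word |
| Isolated Grade 2 bilirubin, Grade 1 or lower after 108 h and by day 7 | Stop | Re-challenge allowed | Contradiction on either meaning |
| Isolated Grade 2 ALT/AST, still Grade 2 at day 7 | Stop | Silent | Gap, not a contradiction |
| Isolated Grade 3 | 96 h / 7 days | 96 h / 7 days | Broadly consistent |
| Concurrent, at the stated ULN thresholds | 96 h / 7 days | 96 h / 7 days | Broadly consistent |

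**The firm case.** The latest time allowed by Section 10.6.2.2 is 96 + 12 = 108 hours (4.5 days). Day 7 is 7 x 24 = 168 hours. The window is 168 - 108 = 60 hours.

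- *Meaning of resolve.* Bilirubin still at Grade 2 at 108 hours is unresolved whether the target is baseline or Grade 1.
- *Clock.* Neither Section 10.6.2.2 nor the Grade 2 row says when time starts; the Grade 3 bilirubin row counts from the start of the dose. The 60 hours assume a common start. If Section 10.6.2.2 instead ran from detection at the 24-hour sample while Table 12 ran from the dose, the limit would be 24 + 108 = 132 hours and the window 168 - 132 = 36 hours. It shrinks but does not close.
- *Wording of the Grade 2 row.* Its condition mentions enzymes although the row also covers bilirubin. Taken literally, an isolated bilirubin rise has ALT and AST below Grade 1 (Table 12, footnote b), so the condition is already met and re-challenge is still allowed.
- *Would a site see it?* Section 10.8.2.5 requires liver tests at least every 48 hours once bilirubin reaches 2 x ULN. That covers the part of Grade 2 from 2 to 3 x ULN. Between 1.5 and 2 x ULN, a test near 96 hours is not scheduled on this ground.

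**The Grade 1 case.** Section 10.8.2.5 describes resolution in two ways: to baseline under clinical chemistry, and to baseline or Grade 1 under liver chemistry tests. Table 12's own Grade 3 ALT/AST row uses Grade 1 or lower for re-challenge but baseline for stopping. Separately, each cycle may start if inclusion criterion 14 is met (Table 9, footnote c). That criterion allows ALT/AST up to 3 x ULN and, without Gilbert's syndrome, bilirubin up to 1.5 x ULN. These are Table 12's Grade 1 limits. On the baseline meaning, Section 10.6.2.2 would therefore also conflict with the cycle-start rule.

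**The trigger.** Pooled monitoring begins after 15 dosed participants (Section 10.4.1). With that denominator, 3/15 = 20.0% is below the threshold and 4/15 = 26.7% is above it. One related stop that depends on which passage a site follows can decide whether review is triggered.

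**The case against.** The best defence is that the Section 10.6.2.2 sentence only summarises Table 12. Its limbs (time limits, clotting, symptoms) match the concurrent-elevation rows. The text before it discusses potential Hy's law events, and it sits between referrals to Section 10.6.1 and to Table 12. Section 10.6.3 also ties restart after hepatic toxicity to Table 12's timeframes. This makes the intention plausible but does not settle the text. The sentence is mandatory and Table 12 is headed as recommended. No passage says which prevails. The referral places Table 12 in Section 10.6.2, and the restart criterion goes on to cite Table 5, which is haematological eligibility.

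Three stronger readings might be inferred, and the documents do not support them:

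- *That the protocol continues dosing throughout Grades 1 and 2 while Section 10.6.2.2 stops it.* At Grade 2, Table 12 makes re-challenge conditional and is silent if the rise is unresolved. The Section 10.6.1 sentence is a general one that leaves liver tests to Table 12.
- *That every lasting Grade 1 rise meets a contradictory stop.* This fails if Grade 1 counts as resolved. Table 12 asks for Grade 1 monitoring only at least weekly, so a 96-hour bilirubin value may not exist.
- *That each such stop costs 1/21 = 4.8 points of ORR.* This requires that the participant would have responded on treatment and does not respond after stopping. SAP Section 5.2.1.1 counts responses after withdrawal from therapy if they precede progression and subsequent anticancer therapy, and Section 10.8.1.2 continues scans after discontinuation.

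**Conclusion.** The point holds in a limited form. There is one firm contradiction (isolated Grade 2 bilirubin reaching Grade 1 or lower after 108 hours but by day 7), one conflict that turns on an undefined word (persistent Grade 1), and one gap (Grade 2 transaminases unresolved at day 7). From Grade 3 for isolated rises, and at the stated ULN thresholds for concurrent ones, the time limits broadly agree.

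The firm window is 60 hours if both clocks start together. How many participants would fall in it is unknown, because the documents give no rate of slow-clearing low-grade rises. They describe the potential Hy's law-type events seen so far as resolving rapidly, but that concerns larger, concurrent elevations. No ORR loss can be quantified.

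What can be said is that an irreversible action would depend on which passage a site follows. That dependence carries into the discontinuation tables and, for related events, the >25% trigger. Crossing the trigger prompts committee review; a pause in enrolment is optional. The matter should be corrected, but it does not undermine the primary analysis.

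**What to change.** Reconcile Section 10.6.2.2 with Table 12. Either state which Table 12 rows (grades, or ULN thresholds for concurrent rises) the 96-hour and 7-day sentence covers, or replace the sentence with a reference to Table 12 once that table carries the rule intended. Define *resolve* once for Section 10.6.2.2, Table 12 and Section 10.8.2.5, and state when the clock starts. State the action for an isolated Grade 2 rise unresolved at day 7. Correct the two cross-references: Table 12's location in Section 10.6.2.2, and Table 5 in Section 10.6.3.

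Which clinical rule applies is for the sponsor's clinical team. The cost is a few sentences in the next amendment or a clarification letter to sites; no statistical method or sample size changes.
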